12.4 Description of the Analyses

For the primary endpoint, the between group effect on weight will be tested using a two-sided t-test (p-value <0.05) of the calculated change in weight from baseline to 12 weeks. This will be conducted using on-treatment data, ie, data from all randomized subjects who completed baseline and 12 weeks evaluations regardless of reported compliance. Similarly, between group differences in insulin resistance measured by HOMA-IR will be determined. A secondary analysis will use analysis of covariance to adjust for the baseline value of the given endpoint.

In the analyses of the secondary endpoints (eg, visceral adiposity, serum lipids, markers of inflammation, hepatic fat content results), two-sided t-test comparing change from baseline to 12 weeks will be calculated between groups. In addition, within group paired t-tests may be performed to determine if, during the 12 week follow up if any of the changes during the randomized intervention portion of the study are sustained after 12 weeks of no intervention.

13 Ethics/Protection of Human Subjects

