6.4 Study Phase (Weeks 1-12)

Interim safety visits will be scheduled for weeks 1, 4, 8, and 12. Subjects will visit the NIH Clinical Center as outpatients. The following assessments and procedures will occur:

- 1. Vital signs including weight and blood pressure
- 2. Physical exam and interval medical history at weeks 4, 8, and 12
- 3. Fasting blood collection for acute care, hepatic, and mineral panels, insulin, glucose and lipids, and CRP, as well as serum, plasma, and PBMCs for storage at weeks 4, 8 and 12. Hgb A1C at week 12. Leptin, ghrelin, PYY, BDNF, inflammatory markers, urine ketones and HIV viral load will be repeated at weeks 4, 8, and 12.
- 4. Nutrition consultation at weeks 4 and 12: Completion of 3-day food diary and waist and hip measurements at weeks 4 and 12
- Review of subject diary documenting compliance and daily steps at weeks 1, 4,
 and 12

- 6. Symptoms Review Questionnaire at weeks 1, 4, 8 and 12
- 7. TFEQ at weeks 4, 8, and 12
- 8. Modified visual analog scales at week 12
- 9. At week 12, baseline assessments will be repeated. Assessments include:
 - Beck Depression Inventory, RAND SF-36, and PANAS questionnaires
 - REE
 - OGTT
 - DXA
 - Blood or urine pregnancy testing for women of childbearing potential
 - Transient elastography with CAP (Fibroscan®, Echosens, Paris, France)

Study visit windows are as follows: Week 1: +/-3 days, Weeks 4, 8, and 12: +/- 7 days.

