6.6 Early Termination Visit

If a subject's participation is terminated before completing the study, then they will be asked to return to the NIH Clinical Center for a Termination Visit. Laboratory tests and study evaluations to be conducted at that visit will be determined on the basis of the subject's health, their willingness, and the appropriateness of the test at that time point.

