11.7 Withdrawal of an Individual Subject

An individual subject will be withdrawn for any of the following:

- An individual subject's decision (the investigator will attempt to determine the reason for the subject's decision.)
- Non-compliance with study procedures to the extent that it is potentially harmful to the subject or to the integrity of the study data.
- Any clinical AE, laboratory abnormality, intercurrent illness, other medical condition or situation occurs such that continued participation in the study would not be in the best interest of the subject.
- The subject loses the capacity to provide ongoing informed consent.
- Development of an exclusion criteria may be cause for discontinuation.

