11.8 Replacement of a Subject Who Discontinues Study Treatment

If a subject withdraws after fewer than 12 weeks on study diet assignment, then they will be replaced. If a subject is replaced, their data will still be included for the safety assessments.

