12.3 Sample Size Justification

Using an alternate day fasting strategy for weight loss in obese adults (n=13), Catenacci et al [57] observed that subjects lost 8.2±0.9 kg (mean ± standard error of the mean) after 8 weeks. For sample size justification, we will use a conservative estimate of 8-kg weight loss after 12 weeks with ICR, and assume 4-kg weight loss among the observation group due to monitoring and counselling through study visits. Therefore, using the standard deviation estimate from Catenacci et al. of 3.24, we will have 96.7% power to detect a 4-kg difference in weight loss between treatment arms with 25 subjects in each arm. With 17 subjects per arm (ie, approximately a 30% dropout rate), the power will be 93.7% to detect a 4-kg difference in weight loss.

In previous studies of ICR, HOMA-IR improvements ranged from 9% to 30%, depending on a number of factors, including the duration of the study, extent and timing of caloric restriction, and whether or not meals were provided [59]. Assuming a baseline HOMA-IR of 1.5, a standard deviation of change in HOMA-IR of 0.25, a study size of

25 subjects per arm, we will have >80% power to detect the difference between a 25% improvement in insulin sensitivity with ICR versus a 10% improvement in the observation arm as measured by HOMA-IR. The power to detect this difference will be 72.1% with 17 subjects per arm.

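### Both primary tests rest on week-12 completers with early leavers replaced, and no planned analysis would correct or bound bias from outcome-related dropout

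*Combined protocol and SAP*

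**What the plan says.** Section 12.4 compares the arms on change in weight from baseline to week 12 with a two-sided t-test at 0.05, using "data from all randomized subjects who completed baseline and 12 weeks evaluations regardless of reported compliance". It labels these data on-treatment. For the second primary endpoint it adds: "Similarly, between group differences in insulin resistance measured by HOMA-IR will be determined". The only other analysis of the primary endpoints is an analysis of covariance on the baseline value.

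Section 11.8 says: "If a subject withdraws after fewer than 12 weeks on study diet assignment, then they will be replaced". It continues: "If a subject is replaced, their data will still be included for the safety assessments". Section 11.7 allows withdrawal for "Non-compliance with study procedures to the extent that it is potentially harmful to the subject or to the integrity of the study data".

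For those who leave early, section 6.6 sets no required measurements: "Laboratory tests and study evaluations to be conducted at that visit will be determined on the basis of" health, willingness and appropriateness at the time.

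Section 12.3 considers dropout only as lost power. Its dropout case begins "With 17 subjects per arm (ie, approximately a 30% dropout rate" and gives 93.7% power for weight and 72.1% for HOMA-IR.

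Section 6.4 states: "Interim safety visits will be scheduled for weeks 1, 4, 8, and 12". Weight is taken at each of these visits, and fasting insulin and glucose at weeks 4, 8 and 12. The interim values have no role in the primary tests.

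**The concern.** Attending week 12 happens after randomisation. Restricting the test to attenders keeps the comparison fair only if leaving is unrelated to outcome, or related to it in the same way in both arms. The plan itself contemplates losing about a third of subjects, yet it has no analysis set of all randomised subjects, no imputation, no repeated-measures model and no sensitivity analysis for missing data. The covariance analysis adjusts for baseline but supplies no missing week-12 value.

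Replacement restores the count of completers, not the comparison that randomisation set up. The text is also unclear about a replaced subject who does attend week 12: section 12.4 would admit that subject, while section 11.8 mentions only safety. If this is settled after the data are seen, the choice could be driven by the result.

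At stake are the estimate and the false-positive rate for both primary endpoints.

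**Working it through.** **1. The plan's own dropout figures.** Inputs from section 12.3: weight difference 4 kg with SD 3.24; HOMA-IR difference 1.5 × (0.25 − 0.10) = 0.225 with SD 0.25; 17 per arm; two-sided 0.05. By the noncentral t distribution the power is 93.7% for weight and 72.1% for HOMA-IR. Both match the plan, so dropout is covered for precision. Dropout is 1 − 17/25 = 32%. (The stated 96.7% for weight at 25 per arm does not reproduce; the same formula gives 99.0%. That is a separate matter and does not affect this point.)

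**2. What replacement would involve.** If leavers were replaced until each arm had 25 completers, 25/0.68 = 36.8, or about 37, would be randomised per arm. That is 74 in all, leaving 74 − 50 = 24 randomised subjects with no stated efficacy use. Section 11.8 does not say that replacement continues to 25 completers.

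**3. Illustration of bias in the weight test.** Every dropout mechanism here is assumed; the documents give no dropout by arm.
- There is no true effect: mean loss is 4 kg in both arms, with week-12 SD 3.24 kg.
- Loss is linear with random slopes, with residual SD 0.8 kg (assumed).
- Visits are at weeks 1, 4, 8 and 12. Everyone attends week 1, and subjects can leave in each of the three later intervals.
- Logit of leaving = a − b × (standardised last observed loss). The intercept a is solved in each arm to give 32% total dropout (−1.99 for b = 0, −2.28 for b = 1, −2.58 for b = 1.5).
- 14,000 simulated trials per case; Monte Carlo error about 0.3 percentage points. A positive difference favours ICR.

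| Dropout depends on | Spurious difference, kg | Type I error, no replacement | Type I error, replaced to 25 completers |
|---|---|---|---|
| Poor loss, ICR only, b = 0.5 | +0.37 | 6.4% | 6.6% |
| Poor loss, ICR only, b = 1 | +0.66 | 9.3% | 11.2% |
| Poor loss, ICR only, b = 1.5 | +0.85 | 12.3% | 16.0% |
| Poor loss, both arms, b = 1 (ICR) and 0.5 (control) | +0.29 | 5.8% | 6.2% |
| Poor loss, both arms equally | 0.00 | about 5% | about 5% |
| Poor loss, control only, b = 1 | −0.67 | 9.3% | 11.2% |
| Large loss, ICR only | −0.67 | 9.3% | 10.6% |

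For the ICR-only, b = 1 case, 20% dropout gives +0.4 kg and 40% gives +0.8 kg. A residual SD of 0.4 or 1.5 kg gives +0.8 or +0.4 kg.

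**4. HOMA-IR.** Let dropout be driven by weight loss (ICR only, b = 1), and assume a correlation of 0.3 to 0.6 between weight loss and HOMA-IR change. The spurious difference is then 0.015 to 0.030 units, which is 7 to 13% of 0.225. Type I error is 5.1 to 5.8%, or 5.3 to 6.9% with replacement.

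**5. What the alternatives recover (ICR only, b = 1).**
- Dropout depends on observed weights: a likelihood-based repeated-measures model is off by 0.02 kg, with type I error of 4.2 to 4.4%.
- Dropout depends on the unseen next weight (not at random): the completer bias is 0.89 kg and the model leaves 0.44 kg.
- Setting leavers to zero change: with equal dropout and equal true means this only multiplies the completer bias by 0.68. That gives 0.68 × 0.66 = 0.45 kg in the first case and 0.68 × 0.89 = 0.61 kg in the second, which is worse than the model it would be checking.

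**6. Power.** When dropout is unrelated to outcome, weight has 93% power with completers and 96% with the model; HOMA-IR has 72% and 71%. For a zero-change analysis under the design effects, the weight difference is 0.68 × 4 = 2.72 kg with SDs √[0.68(3.24² + 8²) − 5.44²] = 4.59 and √[0.68(3.24² + 4²) − 2.72²] = 3.26. For HOMA-IR the difference is 0.68 × 0.225 = 0.153 with SDs 0.270 and 0.218. Power is about 66% and 58% with 25 randomised per arm, and about 83% and 75% with 37.

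**The case against.** The strongest case on the other side has five parts.

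- **The set is close to all-randomised.** Section 12.4 keeps subjects whatever their reported compliance. This stands in part. A reader might infer from the on-treatment label that poor compliers are excluded, but the definition does not say so. Those who stop the diet and attend week 12 are analysed. Section 11.9 likewise asks some subjects to stop restriction and monitors them; it does not withdraw them. The gap is confined to subjects with no week-12 evaluation.
- **The problem would be noticed.** A reader might infer that dropout bias would pass entirely unseen. The documents do not support that. Tolerance and adherence are a secondary endpoint, section 11.7 seeks reasons when a subject decides to withdraw, and interim weights are collected. What is missing is an analysis that corrects or bounds the effect on the estimate.
- **Bias is speculative.** This stands as to size and direction. A reader might infer that the result will favour ICR, since only that arm has two restricted days a week to keep up. But section 6.1 screens with a one-day trial diet, and controls who lose little may also leave. Equal dependence gives no bias, and the larger figures need outcome-related dropout in one arm and random dropout in the other.
- **Replacement up to 25 completers is not in the plan.** This stands. Section 11.8 sets no target, and the documents do not say whether the accrual ceiling of 100 counts screen failures.
- **It is a pilot.** The Précis says so. Even so, section 12.2 states a superiority hypothesis, and sections 12.3 and 12.4 give power and two-sided testing at 0.05.

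**Conclusion.** The concern holds as a risk that the plan leaves unaddressed, not as a demonstrated bias. Both primary tests use week-12 completers, early leavers are replaced with only a safety use stated for their data, and nothing planned would correct or bound the effect of outcome-related dropout. This should be fixed, but it does not invalidate the design.

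The size cannot be derived from the documents. Under the assumed model with 32% dropout in each arm, ICR-only dependence on poor loss gives about +0.4 to +0.9 kg, against a design difference of 4 kg. Type I error is then about 6 to 13%, or about 7 to 16% if leavers were replaced up to 25 completers. Unequal dependence in both arms gives about +0.3 kg and about 6%. Reversed dependence reverses the sign. HOMA-IR is affected less. These figures show what is possible and do not predict what this trial will find.

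**What to change.** **Section 12.4.** Make the primary analysis all randomised subjects in their assigned arm. Use a likelihood-based repeated-measures model for each endpoint (weight at weeks 1, 4, 8 and 12; HOMA-IR at weeks 4, 8 and 12), or equivalent multiple imputation with the interim weights as auxiliary variables. The week-12 arm difference is the estimate. Keep the completer t-test as a sensitivity analysis. Add a not-at-random sensitivity analysis by delta-adjusted imputation (arm-specific, taken to a tipping point) or control-based imputation. Do not rely on zero change for leavers. Report dropout and last observed weight change by arm.

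**Section 11.8.** State that replaced subjects stay in the efficacy analysis and that replacements are newly randomised.

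**Section 6.6.** Record weight and fasting glucose and insulin at termination when the subject agrees, and invite leavers to the week-12 evaluation.

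**Cost.** The change needs protocol wording and two models; the interim visits and the termination visit already exist. The models assume that missingness is explained by observed data, and they only partly correct not-at-random dropout. HOMA-IR gains no power. Subjects who leave before week 4 (about 12 to 13% of each arm in the illustration) add nothing to the HOMA-IR arm difference unless their week-1 weight is used. A joint HOMA-IR and weight model with unstructured covariance has many parameters for about 50 subjects, so multiple imputation or a simpler covariance may be needed.

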Conducted by: National Institute of Allergy and Infectious Diseases and

National Institutes of Health Clinical Center

Principal Investigator: [name], MPH

Sample Size: N = 50; 25 subjects in intermittent caloric restriction arm,

25 subjects in lifestyle modification standard of care arm

Accrual Ceiling: 100

Study Population: Human immunodeficiency virus (HIV)-infected adults aged

18 to 65 with a body mass index ≥30 kg/m² (obese) and at least one feature of the metabolic syndrome (increased waist

circumference, systolic hypertension, dyslipidemia)

Accrual Period: 3 years

Study Design: Randomized study with 2 parallel arms

Study Duration: 5 years (estimated start date of February 2018; end date

January 2023

Intervention Description: Prospective randomized 12-week diet intervention study;

2 days of intermittent caloric restriction (fasting) per week vs

standard of care.

Primary Objective: To evaluate the effects of 12 weeks of intermittent caloric

restriction 2 days per week on weight and insulin sensitivity

in obese HIV-infected individuals with features of the

metabolic syndrome

Primary Endpoint: Changes in weight and insulin sensitivity as measured by

homeostatic model assessment of insulin resistance

(HOMA-IR) between baseline and week 12

Précis

The high prevalence of obesity coupled with chronic inflammation and immune activation places human immunodeficiency virus (HIV)-infected individuals at increased risk for metabolic complications, emphasizing the need for more aggressive management of obesity and related comorbidities in the aging HIV-infected population. The most effective treatment for obesity and metabolic syndrome is lifestyle modification, usually with a combination of caloric restriction and increased exercise. Intermittent caloric restriction (ICR) or intermittent fasting simplifies caloric restriction by severely limiting calories only a few days per week and allowing ad lib diet on the other days. Weight loss benefits are similar to those seen with conventional diets; however, data suggest possible added health benefits from intermittent fasting.

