3.1.1 Study Endpoints

3.1.1.1 Primary Endpoint

Change in weight and insulin sensitivity as measured by homeostatic model assessment of insulin resistance (HOMA-IR) between baseline and week 12.

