12.1 Overview and Design

This is a randomized controlled, study of 12 weeks of ICR versus standard of care. Changes from baseline to 12 weeks in measures of the primary endpoints (weight and insulin sensitivity) and secondary endpoints (eg, hepatic fat content, inflammatory biomarkers) will be compared between the 2 study arms. The 12-week follow-up period after the randomized portion of the study is designed to monitor changes in weight and metabolic parameters after completion of the 2-5 ICR diet arm and the standard-of-care arm.

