12.2 Study Hypotheses

Subjects in the 2-5 ICR group will experience greater weight loss and greater improvements in insulin sensitivity and related metabolic parameters, including decreased visceral adipose tissue and hepatic fat content, compared to subjects in the standard of care arm.

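### Weight and HOMA-IR are both primary with no rule for reading the two tests together; if either result alone may support a primary claim, the false-claim risk is up to 9.75%, and Holm's procedure would hold it at 5% or less almost for free

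*Combined protocol and SAP*

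**What the plan says.** Section 3.1.1.1 defines the primary endpoint as "Change in weight and insulin sensitivity as measured by homeostatic model assessment of insulin resistance (HOMA-IR) between baseline and week 12", and the Protocol Summary has an equivalent definition. Section 12.1 uses the plural: "measures of the primary endpoints (weight and insulin sensitivity".

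The hypothesis in section 12.2 joins the outcomes: "Subjects in the 2-5 ICR group will experience greater weight loss and greater improvements in insulin sensitivity and related metabolic parameters". It goes on to visceral and hepatic fat.

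Section 12.3 powers each primary outcome separately. For HOMA-IR under dropout it states: "The power to detect this difference will be 72.1% with 17 subjects per arm".

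Section 12.4 says that "the between group effect on weight will be tested using a two-sided t-test (p-value <0.05"), using change from baseline to week 12. HOMA-IR follows in one sentence: "Similarly, between group differences in insulin resistance measured by HOMA-IR will be determined". No section gives an alpha split, a testing order or a rule for combining the two results.

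**The concern.** Two primary tests, each at 0.05, give two chances of a false primary finding. Whether that matters depends on a rule that the plan does not state. The text leaves three readings open:

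- **Either result suffices.** Section 12.1 speaks of primary endpoints in the plural, and section 12.4 handles each one on its own. Here the overall error exceeds 5%.
- **Both are required.** Section 3.1.1.1 and the Protocol Summary put both outcomes under one singular heading, and section 12.2 links them with a conjunction. Here there is no inflation, but the chance of success is lower than either power in section 12.3.
- **Weight leads.** Section 12.4 introduces the primary analysis through weight and attaches the 0.05 threshold to weight only. A fixed sequence of weight and then HOMA-IR also causes no inflation, but HOMA-IR then depends on weight being significant.

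If the rule is not fixed in advance, a trial in which only one outcome is significant would have its primary conclusion chosen after the data are seen.

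**Working it through.** **Inputs (section 12.3).** Weight: difference 8 − 4 = 4 kg, SD 3.24. HOMA-IR: baseline 1.5, improvement 25% against 10%, so the difference is 0.15 × 1.5 = 0.225, with SD of change 0.25. There are 25 per arm, or 17 per arm after about 30% dropout. The test is a two-sided two-sample t-test, with power from the noncentral t distribution. The documents give no correlation between the two outcomes, so values of 0 to 0.7 are assumed.

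**Step 1. Reproduce the plan's powers.**

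| Endpoint, n per arm | Stated | At alpha 0.05 | At alpha 0.025 |
|---|---|---|---|
| Weight, 25 | 96.7% | 98.97% | 97.76% |
| Weight, 17 | 93.7% | 93.69% | 88.77% |
| HOMA-IR, 25 | >80% | 87.65% | 80.42% |
| HOMA-IR, 17 | 72.1% | 72.06% | 60.99% |

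Both 17-per-arm figures match an unadjusted 0.05. The 25-per-arm figures do not settle what alpha was planned: more than 80% fits 0.05 and 0.025 alike, and 96.7% fits neither. The 96.7% mismatch is a separate matter and does not affect this point.

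**Step 2. False-claim risk when neither effect is real.**

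- Either suffices, unadjusted: 1 − 0.95² = 9.75% with independent tests.
- Either suffices, Holm (a claim needs the smaller p-value at or below 0.025): 1 − 0.975² = 4.94% with independent tests.
- Both required: 0.05² = 0.25% with independent tests.

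With correlated tests (bivariate normal):

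| Assumed correlation | Either, unadjusted | Either, Holm | Both required |
|---|---|---|---|
| 0 | 9.75% | 4.9% | 0.25% |
| 0.3 | 9.5% | 4.8% | 0.5% |
| 0.5 | 9.1% | 4.6% | 0.9% |
| 0.7 | 8.3% | 4.3% | 1.7% |

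For jointly normal statistics, 9.75% is the ceiling. With no assumption on dependence the ceiling is 0.05 + 0.05 = 10%. Holm stays at or below 5% in every case.

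**Step 3. Only one effect real (25 per arm, independence).** If weight has its planned effect and HOMA-IR has none, the only false claim is HOMA-IR: 5% unadjusted, and 0.025 + 0.025 × 0.9776 = 4.94% with Holm. In the reverse case the figures are 5% and 0.025 + 0.025 × 0.8042 = 4.51%.

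**Step 4. Power with Holm (independence).** Power = P(p ≤ 0.025) + [P(p ≤ 0.05) − P(p ≤ 0.025)] × P(other p ≤ 0.025).

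- 25 per arm, weight: 0.9776 + 0.0121 × 0.8042 = 98.7% (from 99.0%).
- 25 per arm, HOMA-IR: 0.8042 + 0.0723 × 0.9776 = 87.5% (from 87.7%).
- 17 per arm, weight: 0.8877 + 0.0492 × 0.6099 = 91.8% (from 93.7%).
- 17 per arm, HOMA-IR: 0.6099 + 0.1107 × 0.8877 = 70.8% (from 72.1%).

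By simulation at an assumed correlation of 0.7, weight falls to about 98% at 25 per arm and about 90% at 17. HOMA-IR is about 87% and 71%.

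**Step 5. Joint power if both are required (independence).** 25 per arm: 0.9897 × 0.8765 = 86.8%. With the stated 96.7% for weight it is 0.967 × 0.8765 = 84.8%. 17 per arm: 0.9369 × 0.7206 = 67.5%.

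**Step 6. Split results (25 per arm, independence).** Unadjusted, exactly one test is significant in 0.9897 × 0.1235 + 0.8765 × 0.0103 = 13.1% of trials. With Holm, at least one is significant with probability 1 − 0.0224 × 0.1958 = 0.9956, and both with probability 0.8675 − 0.0121 × 0.0723 = 0.8666. The difference is 12.9%.

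**The case against.** The strongest reply is that the inflation depends on a rule that the plan never states. The singular primary-endpoint heading and the joined hypothesis can be read as requiring both results, and section 12.4 can be read as putting weight first; neither reading inflates the error. That stands, and for this reason the point is conditional. It does not close the gap. The hypothesis in section 12.2 also takes in secondary outcomes, so it cannot serve as a decision rule for the two primaries, and section 12.4 states no gate on HOMA-IR.

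Three stronger inferences might tempt a reader, and the documents do not support them:

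- **That the plan runs at 9.75% error.** That figure needs the either-suffices rule, no effect on either outcome and independent tests. If weight truly has its planned effect, Holm changes the false HOMA-IR risk only from 5% to 4.94%.
- **That section 12.3 proves no alpha split was planned.** Only the 17-per-arm figures point to 0.05; the 25-per-arm figures do not decide it. Nor do the powers reveal the success rule, since a both-required rule or a fixed sequence would also test each endpoint at 0.05.
- **That frequent split results call for Holm.** The rate hardly moves, from 13.1% to 12.9%. A written rule for reading a split helps, and that needs no alpha adjustment.

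It is also fair to say that formal error control matters less in a 50-subject pilot. This lowers the stakes, but the plan still sets a 0.05 test and formal power, so the rule should be written down. The 17-per-arm figures are nearer a worst case, because section 11.8 says: "If a subject withdraws after fewer than 12 weeks on study diet assignment, then they will be replaced".

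**Conclusion.** The concern holds in conditional form. The plan has two primary outcomes, tests weight at two-sided 0.05 and HOMA-IR in a like manner, and has no multiplicity control or success rule. Reading the HOMA-IR test as also at 0.05 is an inference from the word linking the two sentences, supported by the 72.1% figure.

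If either result may support a primary claim and neither effect is real, the false-claim risk is 8.3% to 9.75% over assumed correlations of 0.7 down to 0; Holm brings it to 4.3% to 4.9%. Under a both-required or fixed-sequence rule there is no inflation. The powers in section 12.3 are per endpoint and are not wrong on this ground. This is a cheap improvement of modest importance.

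**What to change.** Add to section 12.4, for example:

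> The two primary tests (weight and HOMA-IR) will be judged with Holm's procedure at an overall two-sided level of 0.05: the smaller p-value is compared with 0.025 and, if significant, the other with 0.05. A primary claim will be made only for an endpoint significant under this rule; if only one is, the claim is limited to that endpoint. Both differences will be reported with 95% confidence intervals, which are unadjusted and descriptive and do not by themselves support a claim.

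The last sentence is needed because, when the smaller p-value lies between 0.025 and 0.05, its unadjusted interval excludes zero although Holm allows no claim.

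If both results are meant to be required, state that instead. No adjustment is then needed, and section 12.3 should give the joint power (about 87% at 25 per arm and 67.5% at 17, assuming independence).

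A fixed sequence is suitable only if weight is truly the lead endpoint. Sections 1.1.2 and 1.2 give insulin sensitivity a rationale of its own, which a gate would put at risk. If the true weight difference were 2 kg (assumed; 25 per arm, independence), weight power would be 57.1% unadjusted and 54.8% with Holm. HOMA-IR power would be 0.5709 × 0.8765 = 50.0% behind the gate, against 83.7% with Holm.

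Cost: a few sentences and no more subjects. With independent tests, Holm costs at most 0.3 percentage points of power at 25 per arm. At 17 per arm it costs 1.9 points for weight and 1.3 for HOMA-IR, and the weight loss grows to about 4 points at an assumed correlation of 0.7.

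### HOMA-IR, the lower-powered primary endpoint, is tested on unadjusted change while the planned baseline-adjusted ANCOVA stays secondary, which probably gives up some precision

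*Combined protocol and SAP*

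**What the plan says.** Section 3.1.1.1 names change in weight and change in HOMA-IR, baseline to week 12, as the primary endpoint. Section 12.1 treats both as primary: "Changes from baseline to 12 weeks in measures of the primary endpoints (weight and insulin sensitivity").

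In section 12.4 the effect on weight is to be "tested using a two-sided t-test (p-value <0.05) of the calculated change in weight from baseline to 12 weeks". The next step for the other endpoint is only: "Similarly, between group differences in insulin resistance measured by HOMA-IR will be determined". Adjustment for baseline then follows as a lower-ranked analysis: "A secondary analysis will use analysis of covariance to adjust for the baseline value of the given endpoint". The analysis set is subjects with both baseline and week-12 evaluations.

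Section 12.3 powers HOMA-IR on a baseline of 1.5, "a standard deviation of change in HOMA-IR of 0.25", and a "25% improvement in insulin sensitivity with ICR versus a 10% improvement in the observation arm as measured by HOMA-IR". It gives more than 80% power at 25 per arm and adds: "The power to detect this difference will be 72.1% with 17 subjects per arm". The corresponding figure for weight at 17 per arm is 93.7%. Section 11.8 provides for replacement: "If a subject withdraws after fewer than 12 weeks on study diet assignment, then they will be replaced".

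Section 12.4 does not name the HOMA-IR scale. Raw change is implied by section 12.1, by the cross-reference to the weight test, and by the power figure, which reproduces only in raw units (shown in the working).

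**The concern.** In a two-arm randomized trial, adjusting change for its baseline value targets the same mean difference as the unadjusted comparison. In large samples its variance is never greater. With small arms and no stratification described in section 6.3, it also removes the effect of a chance difference in baseline between arms, which the change t-test leaves in.

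The plan already includes the model and section 6.2 already collects fasting glucose and insulin at baseline, yet the less efficient test carries the primary conclusion. The endpoint that could use the precision is HOMA-IR. At the plan's own 17-per-arm case its power is below 80%, while weight has power to spare. At stake is a somewhat higher chance of missing a real HOMA-IR effect of the planned size. No bias or inflated error rate is at issue.

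**Working it through.** **Inputs.** From section 12.3: baseline HOMA-IR 1.5, improvements of 25% and 10%, SD of change 0.25, and 25 or 17 per arm. From section 12.4: two-sided 0.05. *Assumed, because the documents do not give it:* the correlation r between baseline and week-12 HOMA-IR, with equal variance at the two visits.

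**Step 1. Reproduce the plan's figure.** Difference = 1.5 × (0.25 − 0.10) = 0.225. For the t-test the noncentrality is 0.225 / (0.25 × √(2/n)) with 2n − 2 degrees of freedom.
- n = 17: noncentrality 2.62, df 32, power 72.06% (stated 72.1%).
- n = 25: noncentrality 3.18, df 48, power 87.65% (stated as more than 80%).

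The match at 17 per arm shows that the plan was powered on raw change. Weight at 17 per arm (4 kg, SD 3.24) gives 93.69%, against 93.7% stated.

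**Step 2. ANCOVA of raw change.** With equal variances the residual SD is 0.25 × √((1 + r)/2). The variance of the adjusted difference is residual variance × (2/n) × (1 + t²/(2n − 2)), averaged over chance baseline imbalance, where t has 2n − 2 df. On average the last factor is 1 + 1/(2n − 4). The test has 2n − 3 df.

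Example, n = 17 and r = 0.7: residual SD = 0.25 × √0.85 = 0.2305; standard error ≈ 0.2305 × √(2/17) × √(1 + 1/30) = 0.0804; noncentrality = 0.225/0.0804 = 2.80; df 31; power 77.4%.

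Holding the SD of change at 0.25, each r fixes the baseline SD at 0.25/√(2(1 − r)). Dividing by 1.5 gives the implied coefficient of variation (CV).

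| Assumed r | Implied baseline CV | ANCOVA power, 17 per arm (t-test 72.1%) | ANCOVA power, 25 per arm (t-test 87.7%) |
|---|---|---|---|
| 0.5 | 0.17 | 82.3% | 94.5% |
| 0.7 | 0.22 | 77.4% | 91.7% |
| 0.8 | 0.26 | 75.1% | 90.1% |
| 0.9 | 0.37 | 72.8% | 88.5% |
| 0.95 | 0.53 | 71.7% | 87.7% |
| Baseline unrelated to change | – | 70.6% | 86.9% |

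Break-even is r = 0.93 at 17 per arm (CV 0.46) and r = 0.96 at 25 (CV 0.56). At r = 0.5, 0.7, 0.8 and 0.9, the t-test would need 22, 20, 19 and 18 per arm to match ANCOVA with 17, and 33, 29, 28 and 26 to match ANCOVA with 25. Simulation with 40,000 trials per cell agreed: 81.9, 77.2, 75.0, 73.3 and 71.6% at 17 per arm for r = 0.5 to 0.95.

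**Step 3. Chance imbalance.** At r = 0.7 the implied baseline SD is 0.32, so one standard error of the difference in baseline means at 17 per arm is 0.32 × √(2/17) ≈ 0.11. The slope of change on baseline is r − 1 = −0.3, so the unadjusted contrast moves by about 0.033, or 15% of the 0.225 target.

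**Step 4. Other data models (simulated).** If HOMA-IR is lognormal and effects are proportional, as the percentages in section 12.3 suggest, raw-change ANCOVA against the t-test at CV 0.2, 0.3 and 0.4 gives:
- 17 per arm: 73.8 v 73.1, 77.3 v 73.7, 81.5 v 74.3%.
- 25 per arm: 89.0 v 88.1, 91.0 v 88.5, 93.9 v 88.8%.

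With a lognormal baseline and additive change independent of it, ANCOVA gives 70.7, 70.5 and 70.4% against 72% at 17 per arm. With no arm difference, ANCOVA rejected in 4.7 to 5.1% of trials under the additive-normal and proportional-lognormal models.

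**Step 5. Weight.** At 17 per arm ANCOVA changes power by +0.3, −0.2 and −0.6 point at r = 0.9, 0.95 and 0.98. At 25 per arm the change is within 0.2 point. There is no material gain.

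**Step 6. Log scale.** At 17 per arm, log-scale ANCOVA gives 76.1, 80.9 and 86.9% under the proportional lognormal model (CV 0.2, 0.3, 0.4). It falls to 68.1% (r = 0.8) and 57.2% (r = 0.9) with additive normal variation, and to 65.8, 60.6 and 55.6% with a lognormal baseline and additive change. It is not a safe substitute for the primary analysis.

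**The case against.** Both analyses are valid and pre-specified, so the adjusted estimate will be reported either way; in a pilot study, which one is labelled primary may look like preference. The gain depends on a correlation that the documents do not give, and its sign can reverse: from about +10 points at r = 0.5 to −0.4 at r = 0.95 and −1.5 in the worst case, at 17 per arm. The largest gain needs a baseline CV of only 0.17, which is narrow for entry criteria of any BMI of 30 or more and HbA1c up to 7.0%. At CV 0.30 (r = 0.85) the equal-variance model gives 73.9%, a gain of 1.9 points. Replacement also makes 25 completers per arm the planned case: at 30% dropout this needs 50/0.7, about 72 randomized, against an accrual ceiling of 100. The t-test then has 87.7%.

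Most of this stands and limits the size of the point. It does not reverse it. The equal-variance gain shrinks as CV rises, but under the plan's percentage effects it grows, to 3.6 points at CV 0.3 and 7.2 at 0.4. The documents do not decide between the two models; the possible loss is small in either.

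Two further remarks are fair. The 72.1% in section 12.3 is t-test power and would describe the supportive test after the change. And the claim that both methods target the same difference relies on baseline balance from randomization, which an analysis of completers may weaken; that does not favour the t-test.

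**Conclusion.** The point holds as one of efficiency. Ranking the change t-test above ANCOVA probably gives up some precision for HOMA-IR: about 3 to 10 power points at 17 per arm and 2.5 to 7 at 25 per arm for r between 0.5 and 0.8, and under 1 point at r = 0.9. The top of each range needs an unusually homogeneous baseline. The most that adjustment can cost in these calculations is 1.5 points at 17 per arm and 0.7 at 25.

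These figures rest on the plan's difference of 0.225 and SD of change of 0.25, on an assumed r, and on equal variances for the tabulated values. Confidence in the size is moderate because r is unknown. The gain matters most if replacement falls short and the 17-per-arm case applies. Nothing here applies materially to weight.

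**What to change.** In section 12.4, make the primary HOMA-IR analysis an ANCOVA of change from baseline to week 12 on the raw scale, with treatment arm and baseline HOMA-IR as terms. Report the adjusted mean difference with its confidence interval, and keep the two-sided t-test of change as supportive. State the raw scale explicitly, since section 12.4 leaves it to inference. The same model may be used for weight so that the two primary endpoints match, with no power gain claimed.

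If a percentage-scale result is wanted, pre-specify log-scale ANCOVA (ratio of geometric means) as a sensitivity analysis only. Making it primary would mean restating the endpoint and section 12.3.

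The cost is about two sentences. The model is already planned and the baseline values are already collected. The endpoint and sample size need no change, though a short note in section 12.3 that its power figures are for the unadjusted test would help. The statistical price is one degree of freedom plus the allowance for chance baseline imbalance, already included in the figures above.
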